### **15.4 Planned Interim Analyses**

No interim analyses are planned.

### **15.5 Final Analysis Plan**

Several study populations are defined. The intent-to-treat (ITT) population includes all randomized participants. The modified intent-to-treat (mITT) population includes all participants who received at least one dose of sarilumab or placebo. The second modified intent-to-treat (mITT2) population further excludes the participants with no post-baseline data on the MC-QoL. The third modified intent-to-treat (mITT3) population excludes participants without 16-week MC-QoL data. The per protocol (PP) population only includes all participants with available data on 16-week MC-QoL and who report taking more than 80% of study drug.

The primary analysis will compare the groups with respect to the primary endpoint, the 16-week MC-QoL score in the mITT population using linear regression with an indicator for treatment group and the baseline MC-QoL value as a covariate. While the goal is that all participants will have a 16-week MC-QoL regardless of whether they continue drug throughout, the last observed value of MC-QoL will be carried forward to serve as the primary endpoint in the primary analysis for those participants without 16-week values. (This includes carrying the baseline value

forward, if there are no post-baseline measurements). The test will be two-sided with a 0.05 alpha level.

While the goal is to assess all participants at 16 weeks, regardless of whether they continue with study drug, it is possible that some participants will have missing MC-QoL at 16 weeks. The planned primary analysis, using last observation carried forward, implicitly assumes that study participants who stop getting QoL assessments will be in a stable state, such that the last observed measurement is a reasonable imputation for the 16 week visit. However, to assess the robustness of these results, several sensitivity analysis will be conducted, that implicitly make different assumptions. We will conduct a mixed effects model analysis incorporating all available MC-QoL measurements (this will test the treatment effect at week 16; specifically it will analyze the post-baseline visit timepoints as categorical, and will adjust for the baseline QoL as a covariate.). Another approach imputes participants with missing data at 16 weeks as having the worst scores with a Wilcoxon rank sum test on percent improvement, will be conducted in the mITT population. If there is more than 15% missing data on the 16-week MC-QoL in the mITT population, inverse probability weighting approaches to the linear regression analysis will be done as well in the mITT and ITT populations. Additionally, if the results remain unclear due to missing data, pattern mixture analyses allowing for worse than expected outcomes in those with missing data may be explored.

Other sensitivity analyses will be conducted regardless of whether there are missing data at 16 weeks. We will repeat the primary analysis in the PP population, the mITT2 and mITT3 populations. We will repeat the regression analysis but with a log transformation to both QoL values. To be robust from non-normality, a Wilcoxon rank sum test will also be used to compare the 16-week QoL values in the various analysis populations. Finally, graphical representation of each participant's MC-QoL trajectories over time, color coded by treatment assignment will be constructed.

Baseline adjusted linear regression and Wilcoxon rank sum test will also be used for the secondary and exploratory endpoints. If critical to interpretation, some sensitivity analyses may be conducted.

A 95% confidence interval of the difference in median percentage improvement will be calculated using a bootstrap. Similarly, standard normal 95% confidence intervals for difference in mean 16-week values, and difference in the mean change from baseline values will be presented. Graphical presentations of baseline and 16 weeks values changes will be completed.

Exploratory analyses might consider analyses with additional covariates and results within subgroups.

Analyses of AEs will be descriptive by study arm, and will also consider severity of AEs.

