#### 5.3 Randomization and Blinding/Unblinding Procedures

Eligible participants will be allocated 1:1 to study agent or placebo. A randomization scheme will be generated by the study statistician who will provide a randomized list of arm assignments to the NIH CC Pharmacy. A permuted block approach, with varying block sizes, will be used for the randomization process.

The participants, the investigators, and all who are involved in the evaluation of the study participants including study monitors and central laboratory personnel are blinded to a participant's treatment assignment until all participants have completed the week 16 visit. The NIH research pharmacist is identified as the unblinded third party who will be in charge of treatment assignment, maintaining study supplies/inventory list, and preparing the blinded study medication for each participant. The NIH research pharmacist will be independent of any study assessments. To maintain blinding, any discussion of the treatment assignment between the clinicians and the pharmacy staff is prohibited until the study is unblinded. Unblinding will occur when the final participant completes their week 28 visit (section 6.2.5), or in the case of early termination or study drug discontinuation, after the participant's final study visit.

Participants will be assigned a screening number after completion of the protocol consent for enrollment in the study in the Clinical Research Information Management System of the NIAID (CRIMSON). The study statistician will generate the randomization codes. These codes will be maintained by the NIH research pharmacist. A study allocation number (1, 2, etc) will be assigned when the participant is ready to be randomized. Randomization is defined as the time that the pharmacy is notified that this new participant, with this study allocation number, is being enrolled. This should coincide with the day that the first dose of study drug is administered. Randomization will continue until there are 30 participants who initiate study drug and have at least the first post-baseline QoL measurement at 4 weeks. Note that participants who do not meet these criteria still remain in the study, and attempts to obtain subsequent QoL measures should be made.

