## 15 Statistical Considerations

### 15.1 Study Hypotheses

The primary hypothesis is that the MC-QoL at 16 weeks will be different in the sarilumab-treated participants than in the placebo participants. This is a two-sided alpha = 0.05 test and will be covariate-adjusted by the baseline MC-QoL score.

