### 15.2 Sample Size Justification

The sample size of 15 per arm is limited by the number of patients available to study. In this section, statistical power is evaluated for a possible treatment effect. The distribution of the total MC-QoL measurement was informed by Siebenhaar et al. Since the data are not normally distributed and the scale is constrained between 0 and 100, a beta distribution with parameters 1.30, 2.41 (multiplied by 100), to match the mean and standard deviation of 35 and 22 as seen in Table 7 of Siebenhaar was used to simulate power. This distribution appears quite consistent with the box plot shown in Figure 1 of Siebenhaar. The Siebenhaar paper also reports a high intraclass correlation of 0.9 for measurements 2 weeks apart, suggesting a strong correlation between the baseline and 16-week scores is plausible; thus, a correlation of 0.7 was assumed in the simulation. While the treatment effect is unknown, power was determined under the assumption that the percentage decline in MC-QoL in the sarilumab-treated arm would be 60% and 10% in the placebo arm (some improvement was anticipated in the placebo arm because these individuals know they might be getting an active treatment). As noted previously, this difference between the arms on MC-QoL is considered clinically meaningful.

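### The planned non-normality check drops the baseline score, so its disagreement with the primary test need not mean non-normality; a baseline-adjusted check would be a free improvement

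*Combined protocol and SAP*

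**What the plan says.** Section 15.1 sets the primary test: "This is a two-sided alpha = 0.05 test and will be covariate-adjusted by the baseline MC-QoL score". Section 15.5 specifies the model in the mITT population, "using linear regression with an indicator for treatment group and the baseline MC-QoL value as a covariate".

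The plan expects the scores to be non-normal. Section 15.2 begins its simulation with "Since the data are not normally distributed and the scale is constrained between 0 and 100" and uses "a beta distribution with parameters 1.30, 2.41 (multiplied by 100), to match the mean and standard deviation of 35 and 22".

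Among the sensitivity analyses run whether or not data are missing, 15.5 offers as its remedy for non-normality that "a Wilcoxon rank sum test will also be used to compare the 16-week QoL values in the various analysis populations". No covariate is named, and no rule says how a disagreement with the primary test will be read.

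Three other planned analyses bear on the point:
- The primary regression is repeated with baseline and outcome both on the log scale (15.5).
- Wilcoxon tests are planned for the secondary endpoints (15.5). The first of these is percent improvement in MC-QoL (3.2.2), which uses each participant's own baseline.
- A bootstrap interval is planned for the difference in median percent improvement (15.5).

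**The concern.** A robustness check is easiest to read when it changes only the assumption under test. This one relaxes normality, removes the baseline adjustment and replaces scores by ranks. If the primary regression is significant and the Wilcoxon is not, the natural reading is that the result depends on normality. The cause may instead be that the check has discarded baseline information or lost power through ranking.

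With 15 per arm, one such conflict could colour how a positive result is described. The baseline score is already collected and already used in the primary model, so the ambiguity can be avoided.

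**Working it through.** **Inputs.** From 15.1, 15.2 and 15.5: 15 per arm; two-sided alpha 0.05; scores 100 × Beta(1.30, 2.41); correlation 0.7 on the underlying normal scale; baselines below 25 discarded; declines of 60% and 10%; integer rounding; regression on treatment and baseline. Effects smaller than 60% vs 10% are assumptions.

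**Reproducing the plan.**
- Beta mean: 1.30/(1.30 + 2.41) = 0.350.
- Beta variance: (1.30 × 2.41)/(3.71² × 4.71) = 0.0483, so the SD is 0.220. On the MC-QoL scale these are 35 and 22, as stated.
- The worked example in 15.2 (0.880, 0.642) returns 0.563 and 0.497, as stated.
- After truncation, 61.5% of simulated pairs are eligible and the correlation among them is 0.54.
- Week-16 scores are multiplied by 1 − 0.60 = 0.40 (sarilumab) or 1 − 0.10 = 0.90 (placebo).
- Regression power over 40,000 trials is 99.7%, consistent with the plan's claim of more than 90%.

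**Tests compared on the same trials.**
- Primary: week 16 = b0 + b1 × treatment + b2 × baseline, testing b1 = 0.
- Unadjusted t-test on week-16 scores.
- Planned Wilcoxon on week-16 scores (tie-corrected normal approximation).
- Quade's rank ANCOVA: rank both scores over both arms, regress one set of ranks on the other, compare residuals between arms.
- Wilcoxon on percent improvement.
- Regression on logs, using log(score + 1) at week 16. The +1 is an assumption, because a score of 0 is possible.

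| Power | 60% vs 10% | 50% vs 10% | 40% vs 10% |
|---|---|---|---|
| Primary regression | 99.7% | 95.1% | 73.3% |
| Unadjusted t-test | 98.9% | 89.1% | 60.7% |
| Planned Wilcoxon | 96.5% | 81.5% | 52.6% |
| Quade | 98.5% | 88.8% | 63.4% |
| Wilcoxon, percent improvement | 98.8% | 88.8% | 61.6% |
| Log regression | 97.9% | 85.2% | 57.0% |
| Primary significant, planned Wilcoxon not | 3.3% | 14.2% | 23.0% |
| Primary significant, Quade not | 1.3% | 6.5% | 10.6% |

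Monte Carlo standard error is at most √(0.25/40,000) = 0.25 points. Independent repeats put the Wilcoxon conflict at 3.0 to 3.5%, 14.8 to 15.6% and 22.7 to 24.2%. They put the adjusted-rank conflict at 1.0 to 1.3%, 5.7 to 6.7% and 9.9 to 10.8%. With equal declines of 10%, rejection is 4.9% for the regression and 4.4 to 4.9% for the Wilcoxon, depending on run and continuity correction.

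**Where the power goes.** The split depends on the order in which the two changes are made.
- 60% vs 10%, gap 3.3 points. Through Quade, ranking costs 1.3 and dropping baseline 2.0. Through the t-test, dropping baseline costs 0.8 and ranking 2.5.
- 40% vs 10%, gap 20.6 points. Through Quade, ranking costs 9.9 and dropping baseline 10.8. Through the t-test, dropping baseline costs 12.6 and ranking 8.1.

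**Disagreement without any non-normality.** With exactly normal data, correlation 0.7 and a 0.8 SD shift, the regression is significant and the Wilcoxon is not in 31% of trials, against 7% for Quade. With correlation 0.58, nearer the truncated value, the figures are 22% and 7%.

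**Sensitivity to correlation (0.5 to 0.9).** At 60% vs 10%, the Wilcoxon conflict runs from 6.6% down to 0.3%, and Quade from 5.0% down to 0.0%. At 40% vs 10%, the Wilcoxon conflict rises from 14.3% to 29.8%, while Quade stays between 4.0% and 10.6%.

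**Permutation test of the adjusted coefficient.** In two runs it missed a significant primary result in 0.03% and 0.2% of trials at 60% vs 10%, and in 0.2% and 0.6% at 50% vs 10%. In one run at 40% vs 10% it missed 1.2%. Null rejection was 5.0% and 5.2%.

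**The case against.** A reader might infer that the plan cannot separate non-normality from loss of adjustment, and that this one test decides whether a positive result counts as robust. The documents support neither. Section 15.5 lists the Wilcoxon among several sensitivity analyses and gives it no decisive role. The log regression keeps the baseline covariate, and the percent-improvement Wilcoxon uses baseline with about the same power as Quade (98.8% vs 98.5% at the design effect).

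These two analyses also settle most conflicts. In 20,000 trials per scenario, where the primary was significant and the 16-week Wilcoxon was not, at least one of them was significant in 85% of conflicts at 60% vs 10%, 74% at 50% vs 10% and 71% at 40% vs 10%. At the design effect this leaves 3.5% × 0.15 = 0.5% of all trials unresolved. At 40% vs 10% it leaves 24.2% × 0.29 = 7.0%; another run gave about 6%.

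It is also fair to say that part of the loss comes from ranking, which a rank ANCOVA would keep, and that a permutation test almost always repeats the primary answer. The permutation test confirms that the p-value does not lean on normality; it says little about outliers or scale.

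All of this stands, and it makes the point a modest one. What remains is that the log regression is still a parametric model on another scale, and percent improvement is another endpoint. Neither is a distribution-free test of the baseline-adjusted 16-week comparison.

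**Conclusion.** The point holds as an improvement to a sensitivity analysis. The planned Wilcoxon is valid under the null but does not match the primary comparison, so its disagreement alone does not identify non-normality as the cause. At the plan's own effect the cost is about 3 points of power. At assumed smaller effects it is material: at 40% vs 10%, 23.0/73.3 = 31% of significant primary results would go unconfirmed by the Wilcoxon, against 10.6/73.3 = 14% with Quade.

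The smaller effects are worth considering because 15.2 calls the treatment effect unknown and warns that its power may be overstated. All plan-model figures assume complete data, as the plan's simulation does. No error in the primary test and no bias is shown.

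**What to change.** In 15.5, add one like-for-like distribution-free check in each analysis population: either a permutation test of the baseline-adjusted treatment coefficient, or a rank ANCOVA with ranked baseline. The permutation test isolates the normality assumption, because scale and covariate stay the same. The rank ANCOVA also limits the influence of extreme scores, at some cost in power. Keep the unadjusted Wilcoxon as supportive, and add a clause on how disagreement with the primary test will be read. If permutation is chosen, state the number of permutations and whether they respect the permuted blocks in 5.3.

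The cost is a sentence or two and a few lines of code, settled before treatment codes are opened. No new data are needed, and the primary analysis and sample size do not change.

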### **15.3 Description of the Analyses**

- Safety analysis: descriptive tabulations of AEs will be constructed. These tabulations will also be stratified by severity.
- Efficacy analysis: the primary analysis of the primary efficacy endpoint will compare treatment groups with a regression analysis, adjusted for baseline QoL. A number of sensitivity analyses are planned for the primary analysis if there are participants with missing data at 16 weeks. Baseline adjusted regression analysis and Wilcoxon rank sum tests will also be applied to a range of efficacy endpoints. Descriptive summaries and graphics will also be provided.

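### Section 15.5 does not name the baseline-adjusted treatment coefficient and its interval as the reported primary effect; the mean-difference intervals it promises, read as unadjusted, are less precise

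*Combined protocol and SAP*

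**What the plan says.** Section 15.1 says that the primary comparison "will be covariate-adjusted by the baseline MC-QoL score". Section 15.3 repeats that "the primary analysis of the primary efficacy endpoint will compare treatment groups with a regression analysis, adjusted for baseline QoL", adds regressions and rank tests for other endpoints, and closes with "Descriptive summaries and graphics will also be provided". Section 15.5 compares the 16-week MC-QoL score in the mITT population "using linear regression with an indicator for treatment group and the baseline MC-QoL value as a covariate", sets out how missing week-16 values are filled, and ends: "The test will be two-sided with a 0.05 alpha level".

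Confidence intervals appear only in a later paragraph of section 15.5, after the sensitivity, secondary and exploratory analyses. The first is a bootstrap interval for the difference in median percentage improvement; percent improvement is a secondary endpoint (section 3.2.2, item 1). The others are given as: "standard normal 95% confidence intervals for difference in mean 16-week values, and difference in the mean change from baseline values will be presented".

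That paragraph does not mention the baseline covariate. Elsewhere in section 15 adjustment is written out where it is wanted: the hypothesis, the power calculation, the primary regression, the mixed model and the secondary endpoints.

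**The concern.** The primary p-value will come from one estimator, while the mean-difference intervals promised alongside it come, on a plain reading, from two others. All three estimate the same mean difference in a randomised trial, but the unadjusted ones do not use the information in the baseline score. This matters in a small study: section 15.2 says that "The sample size of 15 per arm is limited by the number of patients available to study". At stake is how precisely and how clearly the size of the effect is reported.

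A smaller question is what *standard normal* means. It may mean ordinary normal-theory limits, in contrast to the bootstrap, or it may mean the multiplier 1.96 taken literally, which is slightly too small at 15 per arm.

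**Working it through.** **Inputs from section 15.2.** MC-QoL is 100 × Beta(1.30, 2.41); the baseline to week-16 correlation is 0.7, set on the underlying normal scale; baselines under 25 are excluded; there are 15 participants per arm; the declines are 60% and 10%; scores are rounded to integers. All participants have week-16 data.

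**Reproducing the plan's figures.**
- Mean: 1.30 / 3.71 = 0.350.
- SD: √[1.30 × 2.41 / (3.71² × 4.71)] = 0.220. These match the stated 35 and 22.
- The worked example also reproduces (0.563 and 0.497).
- Week-16 means among eligible participants are 17.8 and 40.0, so the true difference is 40.0 − 17.8 = 22.2 points.
- Power of the adjusted regression is 99.7%, consistent with the stated figure of more than 90%.

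**Estimators compared on the same simulated trials.**
- Adjusted: the coefficient b₁ in Y₁₆ = b₀ + b₁·treatment + b₂·baseline, with t limits on 30 − 3 = 27 df (multiplier 2.052).
- 16-week: difference in mean Y₁₆.
- Change: difference in mean (Y₁₆ − baseline).

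The last two use an unpooled SE, with either 1.96 or Welch t limits.

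**Results at correlation 0.7 (100,000 trials).**

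| Interval | Variance of estimate | Mean width (points) | Coverage | Disagrees with primary test |
|---|---|---|---|---|
| Adjusted, t | 21.31 | 18.7 | 94.5% | never |
| 16-week, 1.96 | 27.18 | 20.3 | 93.6% | 0.7% |
| Change, 1.96 | 32.40 | 22.1 | 93.9% | 2.2% |
| 16-week, Welch t | 27.18 | 21.7 | 95.0% | – |
| Change, Welch t | 32.40 | 23.2 | 95.0% | – |

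- Variance ratios: 27.18 / 21.31 = 1.28 and 32.40 / 21.31 = 1.52. A repeat with 20,000 trials gave 1.28 and 1.50.
- Width ratios with 1.96: 20.3 / 18.7 = 1.09 and 22.1 / 18.7 = 1.18.
- Width ratios with Welch t limits: 21.7 / 18.7 = 1.16 and 23.2 / 18.7 = 1.24.
- The coverage with 1.96 is what theory predicts: P(|t₂₈| < 1.96) = 0.940, against the correct multiplier of 2.048.

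The gain is smaller than a correlation of 0.7 suggests because dropping baselines under 25 leaves a correlation of about 0.50 in the placebo arm. The textbook variance ratio is then 1 / (1 − 0.50²) = 1.33, close to the simulated 1.28.

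**Range over the correlation.** Section 15.2 cites "a high intraclass correlation of 0.9 for measurements 2 weeks apart", so 0.9 is used as the upper value. The lower value, 0.5, is an assumption made here. Disagreement rates in the 0.5 and 0.9 rows come from 20,000 trials.

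| Correlation | Variance ratio, 16-week | Variance ratio, change | Disagreement, 16-week / change |
|---|---|---|---|
| 0.5 | 1.08 | 1.60 | 1.8% / 11.0% |
| 0.7 | 1.28 | 1.52 | 0.7% / 2.2% |
| 0.9 | 2.14 | 1.60 | under 0.1% / under 0.1% |

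The adjusted estimate has the smallest variance in each row. At 0.5, however, the 16-week interval with 1.96 is no wider than the adjusted one (21.4 against 21.6 points).

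**The case against.** The best reply is that the primary effect is already fixed. Section 15.5 gives the outcome, the population, the treatment indicator, the covariate, the missing-data rule and the alpha level. The coefficient on that indicator is the primary contrast, and any fit returns its SE and interval. The interval paragraph comes after everything else and reads as supplementary, and the phrase *standard normal*, placed after a bootstrap, most naturally means ordinary normal-theory limits. Nor does the adjusted interval win on every measure: it covers 94.5% with a bias of about 0.15 points, because one common slope is fitted, while Welch limits cover 95.0%.

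Most of this stands, and it limits the point to a missing reporting sentence. It does not remove the point, because the plan lists the intervals that it will present and the one matching its primary test is not among them.

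Three stronger readings are tempting and are not supported:

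- **That the plan specifies only a test.** It specifies a regression comparison that defines the effect; only the commitment to report the coefficient with its interval is absent.
- **That the trial throws away sample size.** The ratios 30 / 1.28 ≈ 23 and 30 / 1.52 ≈ 20 describe the supplementary intervals alone. The primary inference uses the covariate and loses nothing.
- **That the intervals would often contradict the primary test.** Under the plan's own assumptions they rarely do. Frequent conflict at the planned correlation would need a smaller treatment effect, and the documents give no such figure.

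**Conclusion.** The point holds as a free improvement in reporting. It is not an error in the primary test, the sample size or the stated power. The size given in the working rests on two things: reading the interval paragraph as unadjusted, which is the plain reading but is not stated outright, and the simulation model of section 15.2 with complete data. The loss for the 16-week difference depends strongly on the correlation and is slight at 0.5; the loss for the change difference is steadier, with a variance ratio of 1.5 to 1.6 throughout. The coverage shortfall of 1 to 1.5 percentage points applies only if 1.96 is meant literally.

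**What to change.** In section 15.5, add that the reported primary effect is the treatment coefficient from the baseline-adjusted regression in the mITT population, with its t-based 95% confidence interval on N − 3 degrees of freedom (27 if N = 30). This interval excludes zero exactly when the primary two-sided test is significant at 0.05, so estimate and test agree by construction.

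Label the unadjusted differences in 16-week mean and in mean change as descriptive, and use t limits for them in place of the phrase *standard normal*. T limits correct coverage only; they widen these intervals and do not improve agreement with the primary test.

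The cost is a sentence or two of text. The coefficient and its SE come from the model already being fitted, and no new data or analysis is needed.

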The simulation of the trial data was performed as follows. The first step was to generate bivariate standard normal variables with correlation of 0.7. Then the cumulative distribution function of each of these was applied to an inverse cumulative distribution function of a beta with parameters 1.30 and 2.41, yielding pairs of Beta (1.30, 2.41) variables with approximate correlation of 0.7. For example, if a pair of bivariate standard normal generated is 0.880 and 0.642, then these values are transformed to 0.563 and 0.497, respectively, as the probability that a Beta (1.30, 2.41) variable is less than 0.563 equals  $\Phi(0.880)$ , and 0.497 is determined likewise. All beta variables were multiplied by 100 to match the MC-QoL scale. The first member of the pair represented the baseline MC-QoL, and since the protocol excludes MC-QoL under 25, pairs with baseline < 25 were then excluded from all simulated trials. Within each replication, 15 eligible pairs were assigned to the active drug arm, and 15 to the placebo arm. The second member of each pair was multiplied by (1 – the assumed decline for their respective treatment group), representing the 16-week MC-QoL value. Finally, to reflect the integer scores of the scale, all baseline and 16-week values were rounded to the closest integer.

Under the above assumptions, the simulation indicated that a baseline covariate adjusted regression analysis of 16-week MC-QoL value has more than 90% power to show that the

sarilumab-treated arm has superior MC-QoL to the placebo arm. It is noted that this power estimate could be too optimistic, as it is based on limited knowledge of and speculation about the distribution of MC-QoL scores, the correlation between baseline and 16 weeks, and the specific nature of the treatment benefit.

Randomization will continue until there are 30 participants who initiate study drug and have at least the first post-baseline QoL measurement at 4 weeks. Note that participants who do not meet these criteria still remain in the study, and attempts to obtain subsequent QoL measures should be made.

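### The two mean-difference intervals in section 15.5 use a standard normal multiplier at 15 per arm; read literally, they cover about 93.4 to 94.1% instead of 95% (minor; supportive intervals only)

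*Combined protocol and SAP*

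**What the plan says.** Section 15.5 (Final Analysis Plan) first gives the difference in median percentage improvement a bootstrap interval. It then states that "standard normal 95% confidence intervals for difference in mean 16-week values, and difference in the mean change from baseline values will be presented". It names no t quantile, degrees of freedom, standard-error formula or covariate for these two intervals, so I take them as unadjusted differences in arm means.

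On size, section 15.2 says "The sample size of 15 per arm is limited by the number of patients available to study", and section 5.3 says "Eligible participants will be allocated 1:1 to study agent or placebo". Section 15.2 adds: "Randomization will continue until there are 30 participants who initiate study drug and have at least the first post-baseline QoL measurement at 4 weeks".

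The primary test is separate. Section 15.1 says "This is a two-sided alpha = 0.05 test", and section 15.5 specifies it as a linear regression of the 16-week score on treatment and baseline MC-QoL.

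**The concern.** A standard normal interval uses 1.96 as though the variance were known. With 15 per arm it is estimated, and the multiplier should be at least 2.048. The plan's effect assumption makes the gap larger for the week-16 score: multiplying scores by 0.4 on sarilumab and 0.9 on placebo gives the arms very different spreads, which lowers the effective degrees of freedom.

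At stake is the accuracy of two published error bars. One is for the raw arm difference in the primary efficacy variable. Section 15.5 names no interval for the baseline-adjusted effect, so these are the only mean-difference intervals it explicitly promises. The error has a known direction: the intervals look slightly more precise than they are.

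**Working it through.** **Inputs**
- Size: 15 per arm, 1:1 (sections 15.2 and 5.3).
- Multiplier: z = 1.960, the literal reading of section 15.5.
- Outcome model, section 15.2: "a beta distribution with parameters 1.30, 2.41 (multiplied by 100), to match the mean and standard deviation of 35 and 22"; "a correlation of 0.7 was assumed in the simulation"; baselines under 25 excluded; scores rounded to integers.
- Effect, section 15.2: "the percentage decline in MC-QoL in the sarilumab-treated arm would be 60% and 10% in the placebo arm". The ratio of week-16 SDs is therefore 0.9/0.4 = 2.25.

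**Step 1: reproduce the plan's own figure.** Rebuilding the section 15.2 simulation (60,000 trials, regression on treatment and baseline, t on 30 − 3 = 27 df) gives power of 99.8%. This agrees with the stated figure of more than 90%, so the model has been rebuilt as described.

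**Step 2: analytic coverage.** For a multiplier of 1.960 on df degrees of freedom, coverage = 2·T_df(1.960) − 1.
- Equal SDs: df = 28, t = 2.048, coverage 94.0%. Width: 1.960/2.048 = 0.957, so z is 4.3% narrower than t (t is 4.5% wider than z).
- SD ratio r = 2.25, Welch–Satterthwaite: df = 14 × (1 + r²)² / (1 + r⁴) = 14 × 36.75 / 26.63 = 19.3. Then t = 2.091 and coverage is 93.5%. Width: 1.960/2.091 = 0.937, so z is 6.3% narrower (t is 6.7% wider).

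**Step 3: simulated coverage under the plan's model, 15 per arm**

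| Declines (sarilumab vs placebo) | Difference in | z | Welch t |
|---|---|---|---|
| 60% vs 10% | week-16 mean | 93.4 to 93.6% | 94.8 to 94.9% |
| 60% vs 10% | mean change | 93.9 to 94.0% | 95.0% |
| 10% vs 10% | week-16 mean | 94.0% | 95.0% |
| 10% vs 10% | mean change | 94.1% | 95.2% |

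The 60% vs 10% rows come from runs of 60,000 and 300,000 trials; the 10% vs 10% rows come from 60,000. The Monte Carlo standard error at 60,000 is √(0.94 × 0.06 / 60,000) ≈ 0.1 percentage point. The shortfall is present with and without a treatment effect.

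**Step 4: width in points.** At 60% vs 10%, the mean half-width goes from 10.15 (z) to 10.83 (Welch) for the week-16 difference, and from 11.04 to 11.59 for change. On average Welch is 6.6% and 4.9% wider; equivalently, z is 6.2% and 4.7% narrower.

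**Step 5: how often the multiplier decides whether zero is excluded.** z excludes zero and Welch does not in about 1% of trials with no effect, about 0.4 to 0.7% at 60% vs 10%, and up to about 4% at 40% vs 10%.

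**Step 6: sensitivity to size (60% vs 10%).** z coverage is 93.2 to 93.8% at 13 per arm, 93.9 to 94.3% at 20, and 94.2 to 94.4% at 30.

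**The case against.** **The wording may not mean z.** Set against the bootstrap in the preceding sentence, the phrase could be loose language for the usual normal-theory interval, which software normally computes with a t quantile. If so, the coverage shortfall disappears and only the wording needs correcting. That reading is possible, but standard normal is the name of the z distribution and nothing in the documents supplies a t quantile. A third reading, a normal interval with a bootstrap standard error, would do worse: about 92.5 to 93.0%. All three readings call for the same clarification.

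**No decision rests on these intervals.** This stands. The test is the adjusted regression, supported by the mixed model, log-scale regression and Wilcoxon analyses. Section 15.5 only commits to presenting the intervals.

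**They might be thought to contradict a planned t test.** A reader might infer that the intervals will clash with a t test of the same unadjusted difference. No such test is planned. The planned t-based test is the baseline-adjusted regression. At 40% vs 10% the unadjusted z interval disagrees with that regression about zero in about 18% of trials, mostly because of the covariate adjustment. A t multiplier would not remove that.

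**15 per arm is not fixed.** Section 12.8.1 allows replacement, and the Protocol Summary sets an accrual ceiling of 60. This also stands, but coverage stays below 95% even at 30 per arm, and a smaller analysis set such as per protocol moves it the other way.

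**Conclusion.** The point holds, as a minor one. Taken literally, the two intervals cover about 93.4 to 94.1% at the planned size, a shortfall of roughly 1 to 1.6 percentage points, and are about 4 to 6% narrower than the correct interval. This rests on the z reading of section 15.5, unadjusted differences, 15 per arm with complete week-16 data, and the section 15.2 outcome model. The lowest figure also needs the multiplicative 60% vs 10% effect; section 15.2 itself warns that its inputs are partly speculative. With equal variances the figure is about 94.0%.

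Three stronger readings are not supported:
- A reader might infer that the primary test is anti-conservative or that the power claim fails. Neither uses these intervals.
- A reader might take every interval in section 15.5 to be affected. The bootstrap interval for the median is not.
- A reader might take 5 to 7% as how far the intervals are too narrow. It is how much wider Welch is than z.

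**What to change.** In section 15.5, replace the standard normal description of the two mean-difference intervals with Welch (unequal-variance) t intervals. Add that any interval taken from the regression uses t critical values on the residual degrees of freedom (27 at 15 per arm with one covariate). If t intervals were always intended, the same edit records it.

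Under the plan's model, Welch restores coverage to 94.8 to 95.2%. The cost is one phrase and intervals about 5 to 7% wider, or about 0.6 to 0.7 point of half-width on the 0 to 100 scale at 60% vs 10% (11.59 − 11.04 = 0.55; 10.83 − 10.15 = 0.68). No change to the sample size, data collection or primary test is needed.
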